14.3.1.3 Oral Treatment Phase (Test Article)

Treatment regimens for po dosing are shown in Table 2. When switching from iv to po test article the recommended interval between doses will be maintained. The first po dose, for both omadacycline and moxifloxacin treatment arms, should be given in the morning 12 to 24 hours after the last iv dose.

The po treatment phase will employ a double-blind, double-dummy design using omadacycline placebo comparator tablets of matching size and shape to active omadacycline tablets and matching over-encapsulated placebo and active moxifloxacin tablets.

To maintain investigator and subject blinding, subjects on both arms will receive 2 tablets and 1 over-encapsulated tablet in the morning as shown in Table 2 below.

Table 2 Treatment Regimens for Oral Test Article

Time of Dosing	Omadacycline Arm	Moxifloxacin Arm	Dosing Condition^{a,b}
Morning	Two 150 mg tablets and 1 over-encapsulated placebo tablet resembling moxifloxacin	One 400 mg over-encapsulated tablet and 2 placebo tablets resembling omadacycline tablets	Fasting overnight (no food or drink except water for at least 6 hours) before dosing; after dosing, no food for 2 hours, no dairy products for 4 hours

^a All doses of po test article should be taken with water.

^b All subjects will be instructed to avoid taking antacids and multivitamins containing multivalent cations (eg, aluminum, magnesium, calcium, bismuth, iron, or zinc) while taking po test article.

When subjects are switched to po therapy, subjects will be given instructions on how to administer the po therapy, a subject diary to record dates and times of po treatment, and a 7-day supply of po test article. Study personnel will review the dosing diary and tablet count with the subject when the po therapy is first dispensed to the subject and at subsequent visits until the subject has completed therapy. Study personnel will review and record which medication is taken in the eCRF.

14.3.1.3.1 Management while on Oral Test Article

While the subject is receiving po therapy, the investigator should assess the subject on study Day 7, 10 and 14 and choose 1 of the following actions:

- continue po test article;

- discontinue test article – this decision will prompt the EOT evaluation.

The date, time and the decision of the investigator will be recorded on source documents and the information transferred to eCRFs by study site personnel.

The investigator may use the culture and susceptibility results from the local microbiology laboratory to help guide therapy; however, decisions to continue or discontinue test article should be based on clinical response rather than susceptibility results (as omadacycline susceptibility testing is not available at the local site). If the CABP is caused by a microorganism that is not susceptible to moxifloxacin *in vitro*, the decision to continue or discontinue study treatment should be based on the subject's clinical course and the investigator's clinical judgment. These cases should be discussed with the Medical Monitor. The rationale for this decision should be recorded in the source documents.

14.3.2 Permitted Dose Adjustments and Interruptions of Test Article

None.

14.4 Follow-up Phase

Subjects will be evaluated at 2 visits after the completion of treatment: at the PTE 5 to 10 days after the last treatment day and at a Final Follow-up assessment 30 to 37 days after the first dose of treatment (see [STUDY FLOWCHART](#)). The Final Follow-up assessment may be conducted via telephone contact or by another interactive technology for subjects who were considered to be Clinical Successes and had no AEs or clinically significant laboratory or ECG abnormalities noted at or after the PTE visit. Otherwise, this assessment is to be performed with an in person study visit.

14.5 Total Volume of Blood Collected

The total volume of blood collected from each subject for this protocol will be up to approximately 170 mL depending on the subject's duration of study participation.

15 TEST ARTICLE AND ADMINISTRATION

Test article will be supplied by Paratek Pharma, LLC (the sponsor). Test article will be labeled according to regulations.

The test article should be administered only to subjects who have provided informed consent and who meet all of the inclusion criteria and none of the exclusion criteria. Once the test article has been assigned to a subject, it must not be reassigned to another subject.

15.1 Test Article Administration

Subjects will be randomized (1:1) to 1 of the following 2 treatment arms:

- Investigational therapy: omadacycline, 100 mg iv q12 h (first 2 doses), followed by 100 mg iv q24h (starting 24 hours after first dose), with the option to switch to 300 mg (two 150 mg omadacycline tablets and 1 over-encapsulated placebo tablet matching moxifloxacin) po q24h after at least 3 days (4 doses) of iv treatment.
- Reference therapy: moxifloxacin, 400 mg iv q24h (with a single placebo infusion to match the omadacycline dosing regimen 12 hours after the first dose on Day 1) with the option to switch to 400 mg (one 400 mg moxifloxacin over-encapsulated tablet and 2 placebo tablets matching omadacycline tablets) po q24h after at least 3 days (4 doses) of iv treatment.

All subjects should receive at least 7 days and at most 14 days (iv and po combined) of test article therapy.

15.1.1 Identity of the Investigational Product

Table 3 **Intravenous Formulation**

A treemap visualization showing the hierarchical structure of Omadacycline's active ingredients. The main category, 'Omadacycline', is represented by a large dark gray rectangle. It is subdivided into several smaller rectangles of varying sizes, representing different components or sub-ingredients. Some of these smaller rectangles are further subdivided into even smaller ones, creating a nested, hierarchical pattern. The overall structure is a complex, multi-layered rectangle.

Table 4 Oral Formulation

Active ingredient	Omadacycline
Strength	100 mg
Form	Tablets

Table 4 **Oral Formulation**

A horizontal bar chart comparing the values of different active ingredients. The y-axis is labeled 'Active ingredient' and the x-axis is labeled 'Omadacycline'. The bars are dark grey. Omadacycline has the longest bar, indicating the highest value. Other active ingredients have shorter bars.

Active ingredient	Value (approximate)
Omadacycline	100
Other active ingredients	10-20

15.2 Investigational and Comparator Test Article

15.2.1 Investigational Test Article: Omadacycline

- 100 mg iv q12 h for first 2 doses followed by 100 mg iv q24h (starting 24 h after first dose)
- 300 mg po q24h after completion of at least 3 days (4 doses) of iv treatment at the discretion of the investigator and meeting minimum criteria for po switch as outlined in [Section 14.3.1.2](#)
- Total treatment duration of 7 to 14 days

15.2.2 Comparator Test Article: Moxifloxacin

- 400 mg iv q24h (with a single placebo infusion to match the omadacycline dosing regimen 12 hours after the first dose on Day 1)
- 400 mg po q24h after completion of at least 3 days (4 doses) of iv treatment at the discretion of the investigator and meeting minimum criteria for po switch as outlined in Section 14.3.1.2
- Total treatment duration of 7 to 14 days

15.3 Subject Compliance while on Oral Test Article

Intravenous administration and compliance will be managed by study personnel prior to switching to po test article. Study personnel at the site, should monitor po test article compliance at each study visit, by comparing the returned test article with the dosing information reported in the subject charts and subject diaries. Compliance and any unresolved discrepancies will be documented in the source document and on the drug inventory record. The test article eCRF

should reflect the reconciled dosing information provided by the subject charts and subject diaries.

16 SAFETY

Any subject who receive test article will be included in the evaluation for safety.

Safety is assessed by the following measures:

- Physical exams
- AEs and SAEs
- Vital signs
- Laboratory assessments
- 12-lead ECG
- Pregnancy assessments

16.1.1 Physical Examinations

After Screening, a physical examination should be conducted on the study days indicated in the **STUDY FLOWCHART** and at the EOT and PTE visits. Any abnormalities or changes in intensity noted during the review of the body systems should be documented in the source documents. If a new clinically significant finding occurs (ie, not noted at Screening) after the Screening exam, it must be captured as an AE. In addition, resolution of any clinically significant abnormal findings that have been reported as an AE will be noted in the medical record and the AE eCRF.

16.1.2 Vital Signs

Vital signs including body temperature, BP, pulse/heart rate, and RR should be recorded prior to each dose while the subject is on iv treatment. Thereafter vital signs should be recorded at all visits, with the exception of the Final Follow-up visit.

- In addition, for the first 3 doses of test article ($t = 0$ hours, $t = 12$ hours, $t = 24$ hours; see **Table 1**) heart rate and BP should be recorded at the following times: just prior to the first infusion, within 30-90 minutes after the start of the first infusion, and again 3.5-5.5 hours after the start of the first infusion.

All vital signs should be captured after 10 minutes \pm 5 minutes of rest while in a non-standing position (supine or semi-recumbent, head of bed from 0° to 90°). Subsequent vital sign measurements should be captured in the same non-standing position.

Systolic and diastolic BP will be measured using an automated validated device, with an appropriately sized cuff.

Pulse will be measured using an automated validated device, when available. If not available, pulse will be measured manually.

In addition to the above, BP and heart rate may be measured whenever clinically indicated at the discretion of the treating physician. Any subject who experiences an AE of non-pleuritic cardiac chest pain, palpitations, or tachyarrhythmia while on study should have an ECG and an evaluation by the investigator (see [Section 16.1.4.1](#)).

Temperature will be obtained using an electronic (rapid reading) device whenever possible.

RR will be determined by observation.

Once the subject is discharged from the hospital, vital signs will be recorded at each return clinical visit by blinded study personnel.

16.1.3 Laboratory Evaluations

Blood samples for hematology, chemistry and coagulation (prothrombin time only) should be drawn at Screening, Day 4, Day 7, Day 10, EOT, and PTE (see [STUDY FLOWCHART](#)). At Screening only, 1 sample will be analyzed at a local laboratory for confirmation of eligibility criteria and a second sample will be shipped to the Central Laboratory for analysis. At all other visits samples should be shipped to the Central Laboratory for analysis.

The Central Laboratory will be used for safety analysis of all specimens collected. Details on the collection tubes and containers, shipment of samples and reporting of results by the Central Laboratory are provided to investigators in the Central Laboratory Manual.

Because subject enrollment will not permit using Central Laboratory results to assess a subject's meeting inclusion/exclusion criteria, it is expected that local laboratory testing will be used in circumstances where this testing is needed to assess a subject's WBC count or differential, serum transaminase or bilirubin levels, serum creatinine or pregnancy testing (for women only).

16.1.3.1 Hematology

The analytes listed in the table below (Table 5) will be measured at the Central Laboratory.

Table 5 Hematology Panel

Hematocrit	White blood cell differential (as % cell counts)
Total red blood cell count	-Neutrophils
Hemoglobin	-Lymphocytes
Mean cell hemoglobin	-Monocytes
Mean cell hemoglobin concentration	-Eosinophils
Mean cell volume	-Basophils
WBC count	
Platelet count	

Table 5 Hematology Panel

16.1.3.2 Clinical Chemistry

The analytes indicated in the table below (Table 6) below will be measured at the Central Laboratory.

Table 6 Clinical Chemistry Panel

Blood glucose	ALT	LDH
Urea	AST	CK
Creatinine	AP	(CK isoenzyme testing as required)
Sodium	Total bilirubin	Calcium
Potassium	Total protein	Phosphate
Chloride	Magnesium	Cholesterol
Bicarbonate	Albumin	Uric Acid
		GGT
		Amylase
		Lipase

ALT = alanine aminotransferase; AST = aspartate aminotransferase; AP = alkaline phosphatase; LDH = lactate dehydrogenase; CK = creatine phosphokinase; GGT = gamma-glutamyl transpeptidase.

16.1.3.3 Other laboratory tests

Table 7 Additional Laboratory Tests

Category	Test	Note
Coagulation	INR	Prothrombin time only
Female endocrinology	β -hCG (for women only)	See Section 16.1.4.2 below. Done both locally (urine) and centrally (serum)

INR = international normalized ratio; β -hCG = beta – human chorionic gonadotropin.

16.1.4 Safety Studies to be Performed Locally

16.1.4.1 Electrocardiogram

A standard 12-lead ECG should be obtained using equipment provided by the sponsor. The ECG will be obtained after the subject has been in a semi-recumbent position for approximately 10 minutes at the following times:

- Screening
- Just prior (within 30 minutes) to the start of the first infusion of the first dose of test article ($t = 0$ h on [Table 1](#))
- 30-90 minutes after the start of the first infusion of the first dose of test article

- Just prior (within 30 minutes) to the start of the first infusion of the third dose of test article ($t = 24$ h on [Table 1](#))
- 30-90 minutes after the start of the first infusion of the third dose of test article
- At the Day 7 visit
- At the EOT visit
- In any case in which a subject develops an AE of non-pleuritic cardiac chest pain, palpitations, tachyarrhythmia or as otherwise clinically indicated (see [Section 16.1.2](#))

Reading and interpretation of the ECG will be performed centrally and provided to the investigator. The investigator is responsible for reviewing interpretations and for retaining hard copies of the reports.

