t = 48 h ^d	omadacycline 100 mg in 100 mL NS 250 mL NS placebo	100 mL NS placebo moxifloxacin 400 mg in 250 mL 0.8% saline
t = 72 h ^e , then q24h ^d	omadacycline 100 mg in 100 mL NS 250 mL NS placebo	100 mL NS placebo moxifloxacin 400 mg in 250 mL 0.8% saline

t = time; NS = Normal saline (0.9% sodium chloride) for injection; q12h = every 12 hours; q24h = every 24 hours.

^a The start time of the first infusion is designated time 0 (t = 0 h), followed by 2 q12h doses (t = 12 h, t = 24 h), and then all subsequent doses are q24h for a minimum of 3 days, 4 doses of iv treatment (through t = 48 h). See [Section 14.3.1.1.2](#) for allowed adjustments in iv dosing schedules.

^b All 100 mL infusions of omadacycline or 100 mL NS placebo are administered continuously over 30 minutes (at least 30 minutes and not more than 45 minutes).

^c All 250 mL infusions of moxifloxacin or 250 mL NS placebo are administered continuously over approximately 60 minutes.

^d At these time points a 100 mL infusion will be administered first, followed by a 250 mL infusion. It is important to follow this sequence of administration.

^e Beginning with the fifth dose (t = 72 h), based on the investigator decision the therapy could be iv or switch to po therapy. Note, the first po dose should be administered in the morning, 12-24 hours after the last iv dose, therefore the first po dose may occur as early as t = 60 h, see [Section 14.3.1.3](#).

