11.1 Adverse Events

Verbatim descriptions of AEs will be coded using Version 17.1 or higher of MedDRA. Summary tables will be provided for all treatment-emergent adverse events (TEAEs) but all AEs will be provided in a listing. A treatment-emergent AE is defined as any AE that newly appeared, increased in frequency, or worsened in severity on or after the initiation of active test article. An AE is considered treatment emergent if the AE start date and time is on or after the start date and time of the first infusion of active test article. If time of the AE is missing and it occurred on the same date as the first infusion of active test article, the AE will be defined as treatment emergent. If the start date of the AE is partial or missing and it cannot be determined if the AE occurred prior to or after the first dose of test article, the AE should be defined as treatment emergent.

Subjects assigned to the moxifloxacin arm receive placebo as their first infusion of test article. The AEs of subjects who experience an AE during this placebo infusion and prematurely discontinue from test article prior to receiving moxifloxacin, will only be presented in a listing.

An overall summary of AEs will include the number of subjects who experienced at least one AE of the following categories: any AE, any TEAE, any drug-related TEAE, any severe TEAE, any serious TEAE, any drug-related SAE, any serious TEAE leading to death, any TEAE leading to premature discontinuation of test article, any TEAE leading to premature discontinuation from the study, any TEAE leading to dose interruption of test article, and any serious TEAE leading to premature discontinuation of test article.

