11.3 Electrocardiogram

A central vendor with readers blinded to treatment assignment will perform the reading of the ECGs. The central ECG results will be used for the statistical analyses.

Descriptive statistics for ECG parameters (heart rate, RR interval, PR interval, QRS interval, QT interval, and QTc interval) at baseline, 30 to 90 minutes after the start of the first infusion of the first and third doses of test article, Day 7 (+1 day), and at the EOT Visit, and the change from baseline will be presented by treatment group. The QTc interval will be presented by both the Bazett ($QTcB = QT/(RR)^{1/2}$) and the Fridericia ($QTcF = QT/(RR)^{1/3}$) corrections. The change from baseline to the minimum and maximum post-baseline values will also be summarized by treatment group. Baseline is defined as the value closest to but prior to the initiation of test article administration. If no value is available prior to the initiation of test article administration, a value within 2 hours after initiation of test article administration.

The number and percentage of subjects with any post-baseline increase in QTcF and any post-baseline increase of > 30 msec or > 60 msec in QTcF will be summarized by treatment group. The number and percentage of subjects with a baseline QTcF ≤ 450 msec and with a post-baseline QTcF of > 450 msec and with a baseline QTcF ≤ 500 and with a post-baseline QTcF of > 500 msec will also be summarized by treatment group. The number and percentage of subjects with a post-baseline increase in QTcF of > 30 msec resulting in a post-baseline QTcF of > 450 msec or > 500 msec will also be summarized by treatment group. A listing will also be provided of subjects with a QTcF that meets one of the criteria listed above and will list all QTcF values for the subject.

The distribution of QTcF values (≤ 450 msec, $> 450 - \leq 480$ msec, $> 480 - \leq 500$ msec, and > 500 msec) at each time point and the distribution of change from baseline in QTcF values at each time point (0 or less [no increase], 1-29 msec, 30-60 msec, and > 60 msec) will be summarized by treatment group.

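### The dose-timed ECGs at doses 1 and 3 fall after the omadacycline infusion but before or during the moxifloxacin infusion, so those QTcF summaries compare the arms at different phases of drug delivery

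*Combined protocol and SAP*

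**What the plan says.** **ECG timing.** Protocol v2.0 section 16.1.4.1 asks for a pre-dose ECG at doses 1 and 3 and for post-dose ECGs "30-90 minutes after the start of the first infusion of the first dose of test article" and "30-90 minutes after the start of the first infusion of the third dose of test article". The other scheduled on-treatment ECGs are "At the Day 7 visit" and at EOT, with no timing relative to a dose. Section 16.1.2 adds a reading at 3.5 to 5.5 hours on the first three doses, but of heart rate and blood pressure only.

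**Infusion order.** Protocol section 14.3.1.1, Table 1, covers t = 0 h and t = 24 h, which are doses 1 and 3: "At these time points a 100 mL infusion will be administered first, followed by a 250 mL infusion". The 100 mL bag holds omadacycline or placebo and is "administered continuously over 30 minutes (at least 30 minutes and not more than 45 minutes". For the second bag, "All 250 mL infusions of moxifloxacin or 250 mL NS placebo are administered continuously over approximately 60 minutes". No time is given for the change between bags.

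**Analysis.** SAP 11.3 summarises ECG parameters and change from baseline by arm at baseline, "30 to 90 minutes after the start of the first infusion of the first and third doses of test article", Day 7 and EOT. It adds by-arm counts of post-baseline QTcF increases above 30 and 60 msec and of values above 450 and 500 msec. Baseline is the last value before test article, a term that includes placebo. SAP 11.1, by contrast, notes for adverse events that "Subjects assigned to the moxifloxacin arm receive placebo as their first infusion of test article" and dates treatment emergence from the first infusion of active drug.

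**The concern.** The ECG clock starts with the first bag in both arms, but the active drug is in the first bag for omadacycline and in the second for moxifloxacin. One nominal window therefore means two different things. In one arm it is mostly the hour after the active infusion; in the other it is the run-in to, or the course of, that infusion.

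QT is a safety question the protocol itself attaches to the comparator: section 13.3 prohibits QT-prolonging co-medication under a heading about interactions with moxifloxacin. If the dose-1 and dose-3 QTcF tables are read at face value, the comparator may look more benign than it is just after infusion, and omadacycline correspondingly less favourable beside it. At dose 1, some moxifloxacin-arm values labelled post-baseline may come from subjects who have so far received only saline.

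**Working it through.** The plan gives no figure of its own here; the check is timeline arithmetic.

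**Inputs** (minutes from the start of the first bag)
- ECG window: 30 to 90, length 60 (protocol 16.1.4.1; SAP 11.3).
- First bag, d: 30 to 45 (Table 1, footnote b).
- Second bag: about 60, no tolerance stated (footnote c).
- Gap between bags: not stated. Taken as 0, then varied.

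**Omadacycline arm.** The active infusion ends at d.
- Share of the window after it = (90 − d)/60.
- d = 30: 60/60 = 100%. d = 45: 45/60 = 75%.
- Longest time from end of infusion to ECG: 90 − 30 = 60 minutes.

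**Moxifloxacin arm, no gap.** The active infusion runs from d to d + 60, so it starts at 30 to 45 and ends at 90 to 105.
- Share before it starts = (d − 30)/60: 0% to 15/60 = 25%.
- Share during it = (90 − d)/60: 75% to 100%.
- Share after it: 0%. The window's upper edge meets the end of infusion only if d = 30 and the ECG is taken at minute 90.

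**Dose infused at the ECG**, at a constant rate, 400 × (x − d)/60 mg at minute x:

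| ECG minute | d = 30 | d = 45 |
|---|---|---|
| 30 | 0 mg | 0 mg |
| 60 | 200 mg | 100 mg |
| 90 | 400 mg | 300 mg |

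If ECG times are spread evenly over the window (an assumption), the mean fraction infused is (90 − d)²/(2 × 60 × 60). For d = 30 this is 3600/7200 = 50%; for d = 45 it is 2025/7200 = 28%. With d also spread evenly over 30 to 45, simulation gives about 39%, with 12.5% of ECGs before moxifloxacin starts. These amounts refer to the current dose only.

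**Sensitivity**
- Gap of 0 to 10 minutes: mean fraction infused about 32%, and about 21% of ECGs before the start.
- A 45-minute bag and a 15-minute gap: start at 60, so (60 − 30)/60 = 50% of the window is before it.
- Second bag of 50 to 70 minutes, no gap: about 0.9% of ECGs fall after the end of infusion.
- Most extreme case (30-minute first bag, no gap, 50-minute second bag): end at 80, so (90 − 80)/60 = 17% of the window is after it.

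**Dose 1 against dose 3.** By t = 24 h a moxifloxacin subject dosed on schedule has already had one full 400 mg dose. The share of ECGs preceding all moxifloxacin therefore applies to dose 1 only.

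**The case against.** The best defence is that the trial's safety objective (protocol 10.2) concerns omadacycline, and the window suits omadacycline well. ECG data are descriptive, with no QT hypothesis. Section 9.1 reports no QT prolongation in Phase 2, in line with a thorough QTc study and hERG work. The tables are given by time point, so a careful reader can see which window each value comes from. This limits the importance of the point, but it does not make the two arms' windows comparable.

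Four stronger readings are tempting, and the documents do not support them.

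- **That all the QTcF counts are biased by a material amount.** The increase and threshold counts use any post-baseline ECG, so Day 7, EOT and clinically indicated ECGs enter too, and SAP 8.6 includes unscheduled assessments in worst-value analyses. Subjects already switched to oral treatment take both products together in the morning, so there is no bag-order asymmetry in their later ECGs. Neither document gives a concentration–QTc relation for moxifloxacin, so milligrams infused cannot be turned into msec.
- **That no moxifloxacin is on board at either timed ECG.** This can be true at dose 1 only.
- **That the end of the moxifloxacin infusion is never observed.** The second bag's duration is approximate, and an untimed ECG could fall there by chance. Essentially never is accurate for the timed ECGs at nominal durations; never is not.
- **That the protocol window must move to the end of the second bag.** With sequential bags, no single clock time is equally placed for both drugs. Moving it would put the omadacycline ECG at least about 60 minutes after its own infusion and give up the only dose-timed ECG close to the end of that infusion.

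**Conclusion.** The timing mismatch stands and follows directly from Table 1 and section 16.1.4.1. At nominal durations with no gap, 75% to 100% of the window is after the omadacycline infusion, while 0% to 25% is before and 75% to 100% during the moxifloxacin infusion. A gap between bags widens the mismatch; a short second bag narrows it slightly. The mean fractions infused rest further on evenly spread ECG times and a constant infusion rate.

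The dose-1 and dose-3 QTcF summaries therefore compare the arms at different phases of active drug delivery. Understatement of moxifloxacin's acute change is the probable direction, not a measured one. The effect on the any-post-baseline counts is diluted and of unknown size. Nothing in the efficacy analyses or the sample size is touched.

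What makes this worth correcting is that SAP 11.1 already recognises the placebo-first infusion for adverse events and SAP 11.3 does not carry the same logic to ECGs.

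**What to change.** In SAP 11.3:

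1. Use the infusion start and stop times, which protocol 14.3.1.1 requires on the eCRF, to classify each dose-1 and dose-3 ECG as before, during or after the active infusion. This assumes that the ECG clock time is held with the central reading; confirm it.
2. Count an ECG as post-baseline in the QTcF change and outlier tables only if it was taken after the first active infusion began. The rule reads the same for both arms and matches SAP 11.1; within the scheduled window it removes only moxifloxacin-arm dose-1 ECGs. Keep those values in the listings.
3. Report the dose-1 and dose-3 QTcF tables with time from the active infusion, and state the between-arm asymmetry as a limitation.

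The cost is one derivation and the loss of some moxifloxacin dose-1 values. With 750/2 = 375 subjects per arm, no gap and evenly spread ECG times, the loss runs from 0 (every first bag 30 minutes) to 0.25 × 375, about 94 (every first bag 45 minutes). Those subjects still contribute their later ECGs. The rule depends on treatment assignment, so it should be fixed before unblinding and applied programmatically, as SAP 6.2.2 does for assignment-dependent population criteria.

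Re-timing the protocol ECG is an optional design trade-off and not part of this fix.
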